2.3 RISK/BENEFIT ASSESSMENT

2.3.1 KNOWN POTENTIAL RISKS

This study poses minimal risk to participants. Possible risks include the following:

- There is potential for false reassurance that the intervention prevents all adverse home environmental exposures.
- Noise produced by the device may be considered by some to be a “white noise” but could be bothersome or harmful if the highest setting is used continuously in close proximity to the child.
- The device may take up space, causing inconvenience.
- Participating individuals could be injured or experience electrical shock during instrument installation or use in the home (childproofing required).

Methods of reducing risk are discussed in Section 2.3.3.

2.3.2 KNOWN POTENTIAL BENEFITS

There is potential for benefit to the research community and future patients. There is the potential benefit to individual participants in decreasing respiratory symptoms, though we cannot estimate the direct impact on the health of the individual participants. Interventions provided in the study can improve the health of individuals living within the home environment, which may be beneficial to household members beyond the child participant (though this endpoint is not studied). HEPA filtration decreases PM in the air to improve IAQ, but we cannot estimate the direct impact on the health of the individual participants and household members.

2.3.3 ASSESSMENT OF POTENTIAL RISKS AND BENEFITS

We do not anticipate significant health risks to participants and will minimize the possible risks described above. The benefit of understanding relationship between the IAQ environment and the health of children with bronchiolitis outweighs the risks. Standard of care medication/treatment will not be altered based on study measurements. To minimize potential risks to participants described in Section 2.3.1:

- The study team will provide education that HEPA filtration will not prevent all adverse environmental exposures. Even though HEPA filtration can improve IAQ, it does not decrease all of the harmful contaminants that can be in the indoor environment. The study team will also emphasize that it is not known if the intervention provides any clinical benefit.
- The HEPA unit chosen produces less noise and takes less space than some other available units. In the recommended “high” setting, the noise generated is below the American Academy of Pediatrics recommendation for sound level in a neonatal intensive care unit⁸¹ and quieter than typical speech and rainfall.⁸² We will instruct parent(s)/guardian(s) not to use the max setting and to set up the filtration unit at least 5 feet from where the child sleeps. In addition, these instructions will be placed on a label attached to the filtration unit.
- The study team will guide equipment setup, maintenance, and safe use (see Section 8.2).

3 OBJECTIVES AND ENDPOINTS

Table 3. Objectives and Endpoints

Study Objectives	Study Endpoints	Justification for Endpoints
Primary		
To determine if use of a HEPA filtration unit home intervention reduces the respiratory symptom burden (symptom-free days; SFD) for 24 weeks compared to a use of a control unit Hypothesis: Children who receive a HEPA filtration home intervention after their first hospitalization with bronchiolitis will have a greater mean number of SFDs over 24 weeks compared to controls.	Number of caregiver-reported SFDs over 24 weeks following the child's first hospitalization for bronchiolitis (SFD defined as a 24-hour period without coughing, wheezing, or trouble breathing)	Children hospitalized for bronchiolitis have a large burden of symptomatic days over the subsequent year after hospitalization, with the majority of the symptom burden occurring over the first 6 months. Clinically, it is important for the intervention to reduce the number of symptomatic days.
Secondary		
1. To test the efficacy of HEPA filtration home intervention, relative to the control arm, on difference in number of unscheduled healthcare visits for respiratory symptoms over 24 weeks Hypothesis: Children who receive a HEPA filtration home intervention after their first hospitalization with bronchiolitis will have fewer unscheduled healthcare visits for respiratory symptoms over 24 weeks (lower number of hospitalizations, ED or UC visits, and other medical visits) compared to the control.	Caregiver reported number of hospitalizations, ED or UC visits, or other unscheduled medical visits for respiratory complaints (cough, wheeze, or trouble breathing)	Children hospitalized for bronchiolitis are prone to recurrent respiratory symptoms. As a result, some children need hospitalization, emergency or urgent care visits, or other unscheduled medical visits for these symptoms. If the intervention can reduce healthcare visits (by reducing respiratory symptoms), this may lead to considerable cost savings.
2. To test the efficacy of a HEPA filtration home intervention, relative to the control arm, on difference in QOL. Hypothesis: Child QOL will be higher in families that receive the HEPA intervention compared to controls.	Total QOL score, as measured by the PedsQL™ Pediatric Quality of Life Inventory Infants Scales questionnaire at the end of the intervention period.	Children hospitalized for bronchiolitis can have decreased QOL post-hospitalization for months or longer due to a variety of factors, including ongoing or recurrent respiratory symptoms, or impact on the family of the experience of the child's severe illness requiring hospitalization. Increased child QOL is expected to follow an intervention that improves respiratory symptoms.
3. To test the efficacy of HEPA filtration home intervention, relative to the control arm, on difference in PM_{2.5} levels in the home over 24 weeks Hypothesis: PM _{2.5} levels will be lower in households that receive the HEPA intervention compared to controls.	Weekly average PM _{2.5} levels as measured by 2 in-home PurpleAir monitors during the 24-week intervention period and scaled to the unit of $\mu\text{g}/\text{m}^3$ per week	To demonstrate that a putative agent causing increased susceptibility to recurrent wheeze in infants is being reduced by active HEPA filtration. PM _{2.5} is one of the most heavily studied criteria pollutants for causing lung disease.

4 STUDY DESIGN

4.1 OVERALL DESIGN

This is a multi-center, parallel, double-blind, randomized controlled clinical trial. Two hundred eighteen children <12 months old with their first hospitalization for bronchiolitis will be randomized 1:1 (stratified by site) to receive 24 weeks of home intervention with active HEPA filtration units to improve IAQ or to a control group without a HEPA or carbon filter inside identical-appearing units. Children will be followed for respiratory symptoms during a pre-intervention period of up to two weeks following randomization and during an intervention period of 24 weeks.

This study is designed to reduce barriers to participation for rural participants in that there will be no required study visits to a distant study site, and all study activities and data collection will be conducted remotely. Participants will be identified in hospitals in ISPCTN states, maximizing the chances that rural and medically underserved populations are represented. It is common for rural children with bronchiolitis to be transferred to tertiary care centers in urban/suburban locales, so inclusion of urban hospitals will allow for recruitment of this population.¹ It is important for rural children to be represented in a bronchiolitis study in order to increase generalizability. Rural and underserved children have a higher risk of decreased access to medical care for symptoms and illness episodes, and a higher burden of asthma.^{83,84} These families may have air pollutant exposure profiles distinct from those residing in urban areas. For example, they might experience less exposure to traffic-related pollutants but may have more wood stove use or exposure to agricultural pollutants or wildfires. With its diversity of sites, the ECHO ISPCTN is well-positioned to enroll rural children that might otherwise be excluded.

Primary Objective:

To determine if use of a HEPA filtration unit home intervention reduces the respiratory symptom burden (symptom-free days; SFD) for 24 weeks compared to the use of a control unit.

Hypothesis: Children who receive a HEPA filtration home intervention after their first hospitalization with bronchiolitis will have a greater mean number of SFDs over 24 weeks compared to children in control arm.

Secondary Objectives:

1. To test the efficacy of a HEPA filtration home intervention, relative to the control arm, on difference in number of unscheduled healthcare visits for respiratory symptoms over 24 weeks.

Hypothesis: Children who receive a HEPA filtration home intervention after their first hospitalization with bronchiolitis will have fewer unscheduled healthcare visits for respiratory symptoms over 24 weeks (lower number of hospitalizations, ED or UC visits, and other medical visits) compared to children in the control group.

2. To test the efficacy of a HEPA filtration home intervention, relative to the control arm, on difference in QOL.

Hypothesis: Child QOL will be higher in families that receive the HEPA intervention compared to controls.

3. To test the efficacy of a HEPA filtration home intervention, relative to the control arm, on difference in PM_{2.5} levels in the home over 24 weeks

Hypothesis: PM_{2.5} levels will be lower in households that receive the HEPA intervention compared to controls.

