
Collect information at 26 weeks (end of 24-week intervention period) by parental report unless otherwise indicated

• Smokers who live in the home (at 26 weeks only, as homes meeting inclusion criteria will be nonsmoking)• Chronic use of asthma medications (inhaled steroid, albuterol)• New prescriptions for asthma medications or antibiotics with healthcare visits for respiratory symptoms (inhaled steroid, bronchodilator, oral steroid, antibiotic) (determined from weekly survey entries)• Atopic dermatitis (has a healthcare provider told you that your child has eczema or atopic dermatitis)• Immunization status (fully immunized, partially immunized, unimmunized per recommendations for age)• Severity scores for pre-intervention symptom days (calculated from study data)• Average number of nights per week away from home (at 26 weeks only; calculated from study data)• Average number of days per week where the child was away from home more than 6 hours (at 26 weeks only; calculated from study data)• Weekly outdoor PM_{2.5} concentration at the U.S. EPA regulatory monitor closest to participant residence and distance in kilometers of nearest U.S. EPA PM_{2.5} monitor determined using ArcGIS. Monitor data will be downloaded from the U.S. EPA's Outdoor Air Quality Data website (https://aqs.epa.gov/aqsweb/documents/data_api.html) (These data may be obtained after the 26-week study period)

Summary of Key Changes from Version-03 to Version-04:

Affected Section(s)	Summary of Revisions Made from V-03 to V-04	Rationale
Protocol Summary 1.1. Synopsis ; 1.2 Schema "During hospitalization;"	
• Changed upper limit for enrollment number FROM 218 TO 228.• Noted that number enrolled is equal to number consented.	
• To account for participants who drop out prior to randomization• To clarify meaning of enrollment.
Protocol Summary 1.1. Synopsis; 3. Objectives and Endpoints Table 3; Section 9.1, Statistical Hypotheses, sub-section "Secondary Objective 3:"	
• Secondary endpoint number 3: Noted that the average PM2.5 levels are the weekly average(s).	Clarification.
1.3 Schedule of Activities table	
• Add reference to MOP.• Added that week 26 means end of participation for subject	Clarification.

Affected Section(s)	Summary of Revisions Made from V-03 to V-04	Rationale

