1 PROTOCOL SUMMARY

1.1 SYNOPSIS

Title:	The BREATHE Study: Bronchiolitis Recovery and the Use of High Efficiency Particulate Air (HEPA) Filters
Study Description:	This is a multi-center, parallel, double-blind, randomized controlled clinical trial. Children <12 months of age hospitalized with bronchiolitis are randomized 1:1 to receive a 24-week home intervention with filtration units containing HEPA and carbon filters (in the child's sleep space and a common room) to improve indoor air quality (IAQ) or to a control group with filtration units without HEPA and carbon filters. The HEPA intervention units and control units will be used for 24 weeks after pre-intervention IAQ measurements. Children are followed for respiratory outcomes over the pre-intervention and intervention periods.
Objectives:	Primary Objective: To determine if use of a HEPA filtration unit home intervention reduces the respiratory symptom burden (symptom-free days; SFD) for 24 weeks compared to a use of a control unit. Secondary Objectives: 
1. To test the efficacy of a HEPA filtration home intervention, relative to the control arm, on difference in number of unscheduled healthcare visits for respiratory symptoms over 24 weeks.2. To test the efficacy of a HEPA filtration home intervention, relative to the control arm, on difference in quality of life (QOL).3. To test the efficacy of a HEPA filtration home intervention, relative to the control arm, on difference in particulate matter ≤ 2.5 micrometers in diameter ($PM_{2.5}$) levels in the home over 24 weeks.
Endpoints:	Primary Endpoint: Number of caregiver-reported SFDs over 24 weeks (SFD defined as a 24-hour period without coughing, wheezing, or trouble breathing). Secondary Endpoints: 
1. Caregiver-reported number of hospitalizations, Emergency Department (ED) or Urgent Care (UC) visits, or other unscheduled medical visits for respiratory complaints (cough, wheeze, or trouble breathing).2. Total QOL score, as measured by the PedsQL™ Pediatric Quality of Life Inventory Infants Scales questionnaire at the end of the intervention period.3. Weekly average $PM_{2.5}$ levels as measured by 2 in-home PurpleAir monitors over 24 weeks and scaled to the unit of micrograms per cubic meter ($\mu g/m^3$) per week.
Study Population:	Up to 228 children consented (enrolled), age <12 months (at admission), with their first hospitalization for bronchiolitis
Phase:	Not applicable

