9.2 SAMPLE SIZE DETERMINATION

Sample Size Justification:

We plan to enroll (consent) up to 228 participants.

To account for an anticipated attrition rate of 16% per arm, the power analysis is based upon a sample size of 196 participants, or 98 participants per arm. From a similar previously published study, it was found the mean of days with symptoms was 70 days (equivalently the mean of SFDs was 98 days out of total 24 weeks or 168 days of observation), and the standard deviation was 43 days.⁵ The proposed sample size will provide 90% power to detect an effect size of 0.465, or a difference of 20 symptom-free days with a standard deviation of 43 days, using a two sample t-test.

Randomization Scheme:

The randomization will be stratified by site. Within each site, participants will be randomized in a 1:1 allocation to receive active HEPA filtration (intervention group) and inactive HEPA unit (control group). Permuted block randomization will be employed.

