## **Section 3. Study Methods**

### **3.1. Study design**

This is a multi-center, parallel, double-blind, randomized controlled clinical trial. Two hundred twenty eight children <12 months old with their first hospitalization for bronchiolitis will be randomized 1:1 (stratified by site) to receive 24 weeks of home intervention with active HEPA filtration units to improve IAQ or to a control group without a HEPA or carbon filter inside identical-appearing units. Children will be followed for respiratory symptoms during a pre-intervention period of up to two weeks following randomization and during an intervention period of 24 weeks. The scientific rationale for the study design is included in the protocol section 4.2. The study biostatisticians from the Data Coordinating and Operations Center (DCOC) will perform statistical analyses.

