## **6. Analysis**

### **6.1. General Considerations**

#### **Timeline for final statistical analysis:**

The final analysis will be performed after data collection and entry is complete on 228 participants and bioinformatics team has completed the data transfer to the study biostatistician.

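### The protocol randomises 218 and the SAP 228; attrition is 16% in one and 14% in the other for the same 228 and 196; and the SAP's final-analysis trigger uses an unlabelled 228

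*Protocol*

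**What the plan says.** **Number randomised.** Protocol 4.1: "Two hundred eighteen children <12 months old with their first hospitalization for bronchiolitis will be randomized 1:1". SAP 3.1 has the same sentence with a different number: "Two hundred twenty eight children <12 months old with their first hospitalization for bronchiolitis will be randomized 1:1". SAP 3.4 divides 228 into 114 per arm.

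**Number consented.** Protocol 9.2: "We plan to enroll (consent) up to 228 participants". The synopsis likewise equates enrolment with consent and caps it at 228. Section 9.2 gives no number randomised.

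**Attrition and evaluable number.** Protocol 9.2: "To account for an anticipated attrition rate of 16% per arm, the power analysis is based upon a sample size of 196 participants", that is 98 per arm. SAP 3.4 describes an initial plan of 218 with 10% loss per arm, then a change to 228 with 14% loss per arm. The target of 196 is the same throughout.

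**Reason for the increase.** SAP 3.4 attributes it to more dropout during follow-up. The protocol's amendment log, used here as context only, gives this reason for raising the enrolment ceiling: "To account for participants who drop out prior to randomization".

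**Final analysis.** SAP 6.1: "The final analysis will be performed after data collection and entry is complete on 228 participants".

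**The concern.** Protocol 4.1 and SAP 3.1 are both operative text, and they give different answers to how many children will be randomised. The SAP says it rests on the protocol finalised on November 29, 2023, and its section 7, reserved for justified departures from the protocol, records none. So the difference is not presented as a deliberate change.

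The attrition rate adds a second inconsistency. The same start (228) and end (196) are joined by 16% in one document and 14% in the other, and both cannot be right. It is also unclear what the rate applies to. A per-arm rate fits randomised children, since a child who has only been consented has no arm, yet protocol 9.2 supplies only a consent ceiling to apply it to.

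The third issue is the SAP 6.1 trigger. The protocol permits fewer than 228 consents, and some consented children may leave before randomisation. If recruitment closes below 228, or if 228 is read as randomised, the rule does not say when the final analysis may start.

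At stake are the recruitment stopping point, the base for the attrition rate, the truth of the 90% power statement and an unambiguous rule for starting the final analysis.

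**Working it through.** **Inputs.** Difference 20 days, SD 43, two-sample t-test, 90% power, 98 per arm (protocol 9.2, SAP 3.4); two-sided 0.05 (protocol 9.4.1); 1:1 allocation (protocol 6.3); 218, 228, 10%, 14% and 16% as located above.

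**Step 1. Reproduce the target.** Normal approximation: n per arm = 2 × (1.960 + 1.282)² × 43² / 20² = 97.1, rounded up to 98. Solving with the t distribution gives 98.1. Power at 98 per arm is 90.0% by the t-test and 90.2% by the normal approximation. The 196 and the 90% reproduce.

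**Step 2. Inflate 196 for loss, N = 196 / (1 − d).**
- d = 0.10: 217.8, so 218. Matches the SAP's initial plan.
- d = 0.14: 227.9, so 228. Matches the SAP's revised plan.
- d = 0.16: 233.3, so 234. Does not match the 228 in protocol 9.2.

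Multiplying instead of dividing, 196 × 1.16 = 227.4, rounds up to 228. That may be how 16% came to stand beside 228, but the protocol does not show its calculation. The loss actually implied by going from 228 to 196 is 1 − 196/228 = 14.0%.

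**Step 3. Work forward, evaluable = N × (1 − d), with t-test power at half that number per arm.**

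| N and loss | Source of the pairing | Evaluable | Per arm | Power |
|---|---|---|---|---|
| 218, 10% | SAP 3.4, initial plan | 196.2 | 98.1 | 90.0% |
| 228, 14% | SAP 3.4, revised plan | 196.1 | 98.0 | 90.0% |
| 228, 16% | Protocol 9.2 | 191.5 | 95.8 | 89.3% |
| 218, 16% | Combined here: 4.1 with 9.2 | 183.1 | 91.6 | 87.9% |

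No passage states the last pairing. It follows only if the per-arm rate in protocol 9.2 is applied to the number randomised in protocol 4.1.

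**Step 4. Can 228 consented and 218 randomised coexist?** Loss before randomisation would be 10/228 = 4.4%. A further 10% after randomisation leaves 218 × 0.90 = 196.2, an overall loss of 1 − 196.2/228 = 13.9%. So they can, but only with 10% loss after randomisation. Protocol 9.2 now says 16% per arm, and SAP 3.1 and 3.4 place the 228 at randomisation.

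**The case against.** The best defence is that protocol 4.1 is not stale. Up to 228 consented, 218 randomised and 196 evaluable form a coherent chain (step 4), and the amendment log's reason for the extra ten children, loss before randomisation, supports it. This stands to the extent that the 228 in protocol 9.2 is a consent ceiling, not a further randomisation target. A reader might infer three competing numbers to be randomised; the documents contain two, 218 and 228. The defence does not remove the conflict with SAP 3.1 and 3.4, and it needs a 10% rate that the protocol no longer gives.

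A reader might also infer from SAP 6.1 that planned attrition makes the final analysis impossible, because 228 children will never all have complete data. The text does not support this. It requires collection and entry to be finished, which can be so for a child who withdrew or was lost; protocol 7.2 and 7.3 provide for recording both, and SAP 6.8 plans for missing surveys. The defect is the fixed, unlabelled 228.

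Nor is the intention-to-treat denominator undefined: protocol 9.3 and SAP 4.1 define it as everyone randomised, so it will be the count actually reached.

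Finally, the power effect is small. That is correct, and it limits the weight of the point.

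**Conclusion.** The point holds as an inconsistency between current texts, with a small numerical effect. The number randomised differs by ten (218 against 228), the attrition rate by two percentage points (16% against 14%), and the 196 evaluable stated in protocol 9.2 does not follow from that section's own 228 and 16%: it gives about 191, with 89.3% power instead of 90.0%. If 16% applies to 218 randomised, the figures are about 183 and 87.9%, roughly two points below target. That lower case is a reading made here and should not be cited as the documents' own figure.

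These results assume a 20-day difference, SD 43, two-sided 0.05, equal arms, a t-test, and that a child lost to attrition contributes no usable primary outcome. Imputation of partly observed children would soften the loss.

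The SAP 6.1 trigger is ambiguous, not unattainable because of attrition. The trial's validity is not in question, but the numbers should be corrected because recruitment, the power statement and the start of the final analysis refer to them.

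**What to change.** 1. In protocol 4.1 and 9.2 and in SAP 3.1 and 3.4, state one set of three numbers: consented (up to 228), randomised, and evaluable. Attach a single attrition rate to the randomised number, and describe any loss between consent and randomisation separately.
2. Restate evaluable n and power to match, without enrolling more. For example, if 228 randomised and 16% are kept, state about 191 evaluable and 89.3% power; if 14% is the intended rate, 196 and 90.0% stand for 228 randomised. Because 228 is a ceiling on consents, 228 randomised also presumes that no consented child is lost before randomisation, and the text should say so or give a lower number.
3. Give one reason for the increase from 218 to 228, since SAP 3.4 and the protocol's log differ.
4. Replace the SAP 6.1 trigger with: when the last randomised participant has completed or left week 26 and the data are locked.

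The cost is wording in both documents, with no change to design, recruitment or data collection.
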